# 14.2. Reporting of Adverse Events and Pregnancies

#### 14.2.1. Reporting Adverse Events

Information regarding occurrence of AEs will be captured throughout the study beginning with signing of the informed consent form (ICF) and ending with Follow-up Visit 3. A qualified clinician (eg, physician, physician assistant, nurse practitioner) will be specifically designated to assess and follow AEs for the subject being treated with adrabetadex. This clinician will probe, via discussion with the subject, for the occurrence of AEs during each subject visit and record the information in the subject's medical record/source documents. Duration (start and stop dates and times), severity/grade (Section 14.1.6), outcome, treatment, relationship to investigational

drug (Section 14.1.7), and any corrective actions taken will be recorded on CRFs. Each AE should also be categorized as "serious" or "non-serious."

#### **14.2.2.** Reporting Serious Adverse Events

Clinical sites will document all SAEs that occur (whether or not related to adrabetadex) in the subject's medical record/source documents *and* on the appropriate CRFs. Information regarding occurrence of SAEs will be captured throughout the study beginning with signing of the ICF and ending with Follow-up Visit 3.

All SAEs will be reviewed by the site clinician, and reported within 24 hours of the site learning of the event. Sites will report applicable SAE information to the sponsor or designee according to the instructions in the Operations Manual.

The site will notify the sponsor or designee of additional information on the SAE, or follow-up information on the initial SAE report, as soon as relevant information is available.

In accordance with the standard operating procedures and policies of the IRB, the site clinician will report SAEs to the IRB.

# 14.2.3. Reporting Pregnancy

The sponsor must be informed within 24 hours upon learning that a subject, or a male subject's partner, has become pregnant any time after the first dose of adrabetadex until 60 days after the last dose of adrabetadex. The pregnancy form should be used to report the pregnancy to the sponsor or designee. The pregnant subject should be discontinued from the study per the exclusion criteria (Section 9.2). Pregnancy is not generally considered an AE; however, subject pregnancies (or pregnancy of a male subject's partner) must be followed until termination of pregnancy or the birth of the child. The pregnancy outcome form should be used to report information regarding the status of the infant and mother.

Patients who become pregnant will be discontinued from treatment.

#### 15. DISCONTINUATION AND REPLACEMENT OF PATIENTS

# **15.1.** Early Discontinuation

A subject may be discontinued from study treatment at any time if the subject, the investigator, or the sponsor feels that it is not in the subject's best interest to continue.

The sponsor has made a determination of a negative benefit/risk balance for adrabetadex. Subjects in this study will be allowed to continue treatment until 20 October 2021 to allow time to start alternative treatment unless there are additional time restrictions mandated by an IRB/EC or health authority.

After 21 June 2021, subjects must be discontinued from the study if the investigator does not consider them to be benefiting from treatment and/or they do not understand the risks associated with adrabetadex, including hearing loss, and that the data from the randomized, controlled trial did not demonstrate significant differences between subjects treated with adrabetadex and shamtreated subjects on any efficacy measures. This discussion should be documented in the subject's medical record and only those subjects (or legally authorized representative) who have demonstrated an understanding of the risk/benefit of adrabetadex treatment should be permitted to continue in the study.

Following the last dose of adrabetadex, subjects will be asked to return to the clinic for a follow-up safety visit. Procedures for the End of Study visit and the safety follow-up visit are noted in Table 5.

If a subject is withdrawn from treatment due to an AE, the subject will be followed and treated by the clinician until the abnormal parameter or symptom has resolved or stabilized.

Reasonable attempts will be made by the clinician to provide a reason for subject withdrawals. The reason for the subject's withdrawal from the study will be specified in the subject's source documents.

# 15.2. Replacement of Patients

Patients who discontinue from the study will not be replaced.

## 16. PROTOCOL DEVIATIONS

A protocol deviation occurs when the subject or clinician fails to adhere to study requirements. Major protocol deviations are those that involve:

- 1. Deviations from the required consent procedure.
- 2. Failure to meet inclusion or exclusion criteria.
- 3. Wrong treatment or incorrect dose.
- 4. Failure to follow any other protocol-specified procedure that, in the opinion of the clinician, sponsor, or sponsor representative, impacts the integrity of the study or puts the study subjects at increased risk.

All major protocol deviations will be reported to the IRB as the IRB regulations dictate.

# 17. DATA MONITORING COMMITTEE

No data monitoring committee will be used in this study.

#### 18. STATISTICAL METHODS AND CONSIDERATIONS

Study data will be summarized using descriptive statistics. No hypothesis testing will be conducted. Descriptive statistics (N, mean, median, standard deviation) will be provided for continuous variables and counts and proportions (N, %) will be provided for categorical variables. All analyses will be based on available data. Missing data will not be imputed.

Data generated in this study may be pooled with others in the adrabetadex clinical program or from historical cohort for comparison. Details of any pooled analysis will be prospectively documented in a separate statistical analysis plan.

## **Summary of Safety Endpoints**

Treatment-emergent AEs (TEAEs) are defined as those AEs that are not present at Day 1 of study or represent the exacerbation of a pre-existing condition during the treatment period.

All AEs reported in this study will be coded using version 23.1 of the Medical Dictionary for Regulatory Activities (MedDRA®). Coding will be to lowest level terms. The verbatim text, the preferred term, and the primary system organ class will be listed.

Summaries of all TEAEs by treatment group will include:

- The number (n) and percentage (%) of subjects with at least 1 TEAE by system organ class and preferred term.
- TEAEs by severity, presented by system organ class and preferred term.
- TEAEs by relationship to treatment (related, not related), presented by system organ class and preferred term.

Deaths and other SAEs will be listed and summarized. TEAEs leading to permanent treatment discontinuation will be listed and summarized.

Laboratory test results will be summarized by baseline and change from baseline to each scheduled assessment time with descriptive statistics. Shift tables based on baseline normal/abnormal and other tabular and graphical methods may be used to present the results for laboratory tests of interest. Listings will be provided with flags indicating the out of laboratory range values.

Vital signs (body temperature, pulse rate, blood pressure, and respiration rate) will be summarized by baseline and change from baseline to each scheduled assessment time with descriptive statistics.

Changes in audiologic testing will be summarized by visit based on accumulated data at the time of analysis.

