# 7. TREATMENT AND ASSESSMENT PLAN

# 7.1. Study Design

This is a prospective, open-label study to evaluate the longer-term safety of adrabetadex in subjects with neurological symptoms of NPC type C disease. The study is anticipated to enroll approximately 60 subjects from 30 sites in the US. Eligible subjects will receive adrabetadex intrathecally (IT) via lumbar puncture (LP) every 2 weeks, and assessments of safety measures will be performed at prescribed intervals. Patients who have not previously been treated with adrabetadex will start at a dose of 400 mg, and subjects who have been previously receiving adrabetadex will receive their current stable dose of adrabetadex.

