# 9.1. Inclusion Criteria

To be included in the study, subjects must meet the following criteria:

- 1. Male or female and at least 4 years of age at time of screening.
- 2. Has a confirmed diagnosis of NPC and exhibits neurologic symptoms.
- 3. Patient or parent/guardian must provide written informed consent to participate in the study. In addition to parental consent, assent to participate must also be sought from minor children.
- 4. Has the ability to undergo LP and IT drug administration.
- 5. If taking miglustat (Zavesca®), must have been on a stable dose for the past 6 weeks and be willing to remain on a stable dose for the duration of participation in the study. Alternatively, subjects may elect to discontinue miglustat use and be eligible for entry into the study after undergoing a minimum 6-week washout period prior to study Day 1.
- 6. If there is a history of seizures, the condition must be adequately controlled, ie, the pattern of seizure activity must be stable and the subject must be on a stable dose and regimen of antiepileptic medication during the 1 month prior to Screening, with no change in dose or regimen up to and including the day of the first dose of adrabetadex (Day 1).
- 7. If not currently receiving adrabetadex, agrees to discontinue any other investigational treatments for at least 1 month prior to first dose of adrabetadex (Day 1); subjects who are currently receiving intrathecal adrabetadex are eligible to participate.
- 8. Sexually active females and males must use a medically acceptable method of contraception and must agree to continue use of this method for the duration of the study and for 30 days after participation in the study. Acceptable methods of contraception include barrier method with spermicide, intrauterine device, steroidal contraceptive in conjunction with a barrier method, abstinence, or same-sex partner.
- 9. Patient or parent/guardian must possess the ability, in the clinician's opinion, to understand and comply with study requirements, including clinical outcome measurements and instructions, for the entire duration of the study.
- 10. Caregiver, parent, guardian, or responsible adult must be able and willing to accompany the subject to study visits.

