#### 12. STUDY PROCEDURES AND GUIDELINES

A schedule of assessments and procedures by time point is presented in Section 22.

Prior to conducting any protocol-related activities, written informed consent must be signed and dated by the subject or the subject's legal representative. If appropriate, assent must also be obtained prior to conducting any protocol-related activities.

Patients who have been screened, meet eligibility criteria, and have provided signed written informed consent will be enrolled. Baseline assessments will be completed at Screening, as described in Table 4.

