#### 12.2.2. Adverse Events

Information regarding occurrence of AEs will be captured throughout the study, beginning with the signing of informed consent and ending after procedures for Follow-up Visit 3. Information will be recorded on the appropriate CRFs. Definitions associated with AEs and the procedures for reporting them are presented in Section 14.1 and Section 14.2, respectively.

Any time a subject has a reported AE of special interest, ie, AE related to hearing impairment (National Cancer Institute Common Terminology Criteria for Adverse Events [CTCAE] grade 3 or higher), audiologic assessments need to be conducted. Audiologic assessments may also be conducted at the discretion of the investigator for hearing impairment AEs of CTCAE grade < 3(Section 12.2.6.1, Section 14.1.8).

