#### 14.1.1. Adverse Event

An AE is defined as any untoward medical occurrence associated with the use of a drug in humans, whether or not considered drug related (Code of Federal Regulations [CFR] Title 21 Part 312.32).

An AE can therefore be any unfavorable and unintended sign (including an abnormal laboratory finding), symptom, or disease temporally associated with the use of the drug, without any judgment about causality (GCP definition).

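### The only TEAE definition has no onset condition in its first part, so read literally an AE that starts and resolves during screening counts as treatment-emergent (minor)

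*Combined protocol and SAP*

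**What the plan says.** Section 18 (Summary of Safety Endpoints) contains the only definition of a TEAE: "those AEs that are not present at Day 1 of study or represent the exacerbation of a pre-existing condition during the treatment period". Elsewhere the term is only expanded as an abbreviation or named as an endpoint. Section 18 mentions a separate analysis plan only for pooled analyses.

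The other relevant provisions are:

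- **Collection window.** Section 12.2.2 captures AEs "beginning with the signing of informed consent". Section 14.2.1 and the footnotes to Tables 4 and 5 agree. Table 4 marks AE collection at Screening, which spans Day −45 to Day −1.
- **What an AE is.** Section 14.1.1 describes an AE as a sign, symptom or disease "temporally associated with the use of the drug". It gives no onset rule relative to the first study dose.
- **Data available.** The CRF items in Section 14.2.1 include "Duration (start and stop dates and times".
- **Prior exposure.** Under Section 7.1, "subjects who have been previously receiving adrabetadex will receive their current stable dose of adrabetadex". Table 4, footnote a, lets subjects already on the drug be screened and dosed on the same day.
- **Use.** TEAEs are the first item of the primary endpoint (Section 6). Section 18 tabulates them by system organ class and preferred term, by severity and by relationship to treatment.

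**The concern.** A treatment-emergent event is meant to be one that appears or worsens once study treatment has begun. The first alternative in the definition does not say so. It compares the event with a single time point, Day 1, and an event that is already over by then passes the test just as well as one that has not yet started. The words that refer to the treatment period belong to the second alternative, on exacerbations.

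Because AEs are recorded from consent, such events will be in the database, and nothing in the plan removes them before the TEAE tables are built. Readers of those tables would take them as having emerged on adrabetadex. Two programmers could produce different primary safety tables and both claim to have followed the plan. Section 18 also allows the data to be pooled or compared with a historical cohort, where an unclear TEAE flag could carry over.

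**Working it through.** **Step 1. The definition against each possible timing**

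| AE timing | As written | With an onset rule |
|---|---|---|
| Starts and resolves in screening | TEAE (absent at Day 1) | Not a TEAE |
| Starts in screening, ongoing at Day 1, does not worsen | Not a TEAE | Not a TEAE |
| Ongoing at Day 1, worsens on treatment | TEAE | TEAE |
| Starts after Day 1 | TEAE | TEAE |

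Only the first row is misclassified.

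**Step 2. How large could it be?** The plan gives no figure to reproduce, so this is a sensitivity calculation.

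Inputs from the documents: maximum screening length L = 45 days (Table 4) and about 60 subjects (Section 7.1). Week 26 is the first 6-month time point, and Table 5 lists visits to Week 208 and beyond.

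Assumptions: AEs follow a Poisson process at r = 1, 2 or 4 per patient-year, with the same rate in screening and on treatment. Durations are exponential with mean d = 7 or 30 days. Every subject uses the full 45 days. T is follow-up in days.

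Formulas:

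- Effective screening days in which an AE can start and also resolve: E = L − d(1 − exp(−L/d)). For L = 45, E = 38.01 (d = 7) or 21.69 (d = 30).
- Probability of at least one such AE: P = 1 − exp(−rE/365).
- A subject is wrongly added only if no true TEAE occurs: inflation = P × exp(−rT/365).

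Example, r = 2, d = 7, T = 182: P = 1 − exp(−2 × 38.01/365) = 0.188; exp(−2 × 182/365) = 0.369; product 0.069, or 6.9 points on a true incidence of 63.1%.

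Example, r = 1, d = 7, T = 728: 0.0989 × 0.1361 = 0.01346, or 1.3 points.

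Inflation in percentage points (d = 7 / d = 30):

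| r | 26 weeks | 52 weeks | 104 weeks | 156 weeks |
|---|---|---|---|---|
| 1 | 6.0 / 3.5 | 3.6 / 2.1 | 1.3 / 0.8 | 0.5 / 0.3 |
| 2 | 6.9 / 4.1 | 2.6 / 1.5 | 0.3 / 0.2 | 0.0 / 0.0 |
| 4 | 4.6 / 2.9 | 0.6 / 0.4 | 0.0 / 0.0 | 0.0 / 0.0 |

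At 26 weeks, 2.9% to 6.9% of 60 is about 2 to 4 subjects.

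**Step 3. Less extreme inputs**

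- 14-day screening (E = 7.95 or 2.81): 0.4 to 1.6 points at 26 weeks and 0.1 to 0.8 at 52 weeks.
- On-treatment rate double the screening rate, 45 days: 0.4 to 3.6 points at 26 weeks and 0.0 to 1.3 at 52 weeks.
- Same-day screening and dosing: zero. If half of subjects are handled this way, every figure halves.

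**Step 4. Single preferred terms.** For a term with true rate q, inflation is [1 − exp(−q(T+E)/365)] − [1 − exp(−qT/365)]. With q = 0.05 to 0.2 per patient-year and 45 days, a row rises by 0.3 to 1.9 points at 26 weeks (11% to 21% relative), 0.3 to 1.7 at 52 weeks (5% to 10%) and 0.3 to 1.4 at 104 weeks (2% to 5%). For rare terms the relative inflation tends to E/T.

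**The case against.** The best defence is that the sentence defines treatment-emergent events, so absence at Day 1 is plainly a baseline comparison: absent then, present later. Most programmers would add an onset rule unprompted. The reference to the treatment period might also be read as closing both alternatives. That reading is strained, and the treatment period is not defined, so it leaves the text open rather than settled. The likely good sense of a programmer limits the harm but does not supply the missing rule.

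Second, the general AE definition ties AEs to use of the drug, which could be said to exclude pre-dose events in treatment-naive subjects. Explicit collection from consent, with no such filter, weakens this.

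Third, the population at risk is narrow, and this stands. Subjects already on adrabetadex may have no screening interval. If they have one, they are already exposed, so a screening event in them is not an off-drug event. The documents do not give the split between naive and previously treated subjects.

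Fourth, the larger figures apply the maximum screening length to everyone over a short follow-up. This also stands: Section 18 sets no 26-week TEAE analysis, and the objective is longer-term safety.

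A reader might also infer that reactions starting on Day 1 after the dose are excluded because they are present on that day. The documents do not support giving this weight. Criterion 6 of Section 9.1 identifies Day 1 as the day of first dose, and the natural meaning of a Day 1 baseline is the state before dosing.

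**Conclusion.** The definition is wrong as written, and the point is minor. The conclusion about the wording is firm: the first alternative has no onset condition, AEs are collected from consent, and no other text removes events that ended before the first study dose. Treatment-naive subjects are the clear case.

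The size is unknown. The calculated ranges rest on assumed rates and durations and on 45 days of screening for all, so they mark the upper end for those rates. They shrink quickly with longer follow-up. Single preferred-term rows shrink more slowly than the overall share.

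A reader might infer that the primary safety results are materially distorted. The documents do not support that. No hypothesis is tested, deaths and SAEs are summarized without a TEAE filter, AEs are listed, and audiologic change is summarized separately by visit. No data are lost, and recorded start dates and times allow any misclassified event to be found and corrected.

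**What to change.** Replace the definition with one based on onset. A TEAE is an AE that begins, or a pre-existing condition that worsens, at or after the date and time of the first adrabetadex dose in this study and up to a stated end of window. For previously treated subjects, say that the anchor is the first dose in this study, not first-ever exposure. List AEs between consent and that dose separately.

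The end of window could be Follow-up Visit 3, where Sections 12.2.2 and 14.2.1 end AE collection. Table 6 shows a single follow-up visit, so the end point chosen should be tied to a visit that the schedule defines.

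Count a Day 1 AE with no start time as treatment-emergent. State this as a classification convention next to the Section 18 rule against imputing missing data.

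The cost is a reworded definition and one programming rule. No new data are needed, and enrolment is already closed, so only the analysis changes. The downside is that a few pre-dose Day 1 events without a start time may be counted as TEAEs.

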Vtesse has been provided data from 3 subjects being treated under an iIND at Rush University Medical Center who have been receiving IT VTS-270 every 2 weeks, the dosing regimen used in the *NPC1* mutant cat model that was shown to improve neurologic symptoms and improve survival. It is important to note that this regimen is different from that employed in the National Institutes of Health phase 1/2a study, where subjects are dosed once a month.

In the proposed study, it is expected that subjects may experience some degree of nonreversible hearing loss; how much of this hearing loss may be attributable to NPC1 disease progression, which occurs in approximately 64% of subjects, versus study drug toxicity is not ascertainable at the present time. At this stage of clinical development, apart from animal model data and uncontrolled clinical reports, there is at present only a theoretical benefit and a known risk of ototoxicity in those subjects randomized to study drug. However, given the fatal and irreversible nature of NPC1, the continued clinical evaluation of efficacy, despite potential drug-related ototoxicity and in the absence of other known dose-limiting AEs or SAEs, is supported, only in those subjects (or legally authorized representative):

- who appear to be benefiting from intrathecal adrabetadex based on the investigator's assessment, AND
- who are aware of the risks associated with adrabetadex, including hearing loss, and understand that no significant differences were seen between subjects treated with adrabetadex and sham-treated subjects on any efficacy measures in this randomized, controlled trial

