<sup>m Prior to each dose escalation, an audiology examination should be performed (within 72 hours) to assess for hearing impairment. If hearing impairment is observed, dose escalation should not proceed. An audiology examination should also be performed within 72 hours prior to the subsequent visit following a dose escalation (with results available at the study visit) to see if the subject can continue at the same dose.

<sup>n Collected from treatment-naïve subjects only. Red blood cell count, white blood cell count, white blood cell differential, glucose, and protein.

<sup>o Any medications used to treat NPC in the past (no time limit) and any other medications taken within 30 days of the Screening Visit will be recorded at the Screening Visit.

Table 5: Schedule of Assessments and Procedures – Week 28 and Thereafter, Including End of Study/Early Termination

Window (weeks)	(± 1)	(± 1)	(± 1)	(+1)
Frequency (starting at Week 28) or Time Point	Every 2 Weeks After 1st Dose (Weeks 28, 30, 32, etc.)	Every 6 Months After 1st Dose (Weeks 52, 78, 104, 130, 156, 182, etc.)	Additional Assessment Every 12 Months After 1st Dose (Weeks 52, 104, 156, 208, etc.)	End of Study/ Early Termination
Procedure				
Clinician-CGIC assessment a		_b		
NPC-SS Intake a		_b		
EQ-5D-3L assessment a		_b		
Weight	X	X		X
Vital signs c,b,d	X e	X e		
Abbreviated physical examination		X		X
Urinalysis		X		X
Urine pregnancy test		X		X
Neurological examination f		X		X
Audiologic testing g		X		X
Diagnostic threshold auditory brainstem response h		_h	-h	_h
Blood for clinical laboratory tests i,i		X		X
Blood for plasma bile acids k,j		_b		
LP and adrabetadex administration k	X	X		
Adverse events d	X	X		X

Window (weeks)	(± 1)	(± 1)	(± 1)	(+1)
Frequency (starting at Week 28) or Time Point	Every 2 Weeks After 1st Dose (Weeks 28, 30, 32, etc.)	Every 6 Months After 1st Dose (Weeks 52, 78, 104, 130, 156, 182, etc.)	Additional Assessment Every 12 Months After 1st Dose (Weeks 52, 104, 156, 208, etc.)	End of Study/ Early Termination
Procedure				
Concomitant medications/therapies d	X	X		X

All subjects who discontinue protocol treatment will be requested to return to the clinic to complete an Early Termination Visit.

Note: Any assessment done every 6 months is, by definition, done every 12 months.

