- a The efficacy assessments (Clinician-CGIC, NPC-SS, and EQ-5D-3L) should be performed *prior to other assessments and procedures*. In addition, the Clinician-CGIC should be conducted prior to other efficacy assessments.
- b Procedure(s) should not be performed starting when the protocol amendment is approved by the respective IRB/Ethics Committee.
- c Vital signs (blood pressure, pulse rate, respirations, and body temperature) will be recorded following a 5-minute rest in supine position.
- d The collection period of adverse events, and concomitant medications will begin after informed consent is obtained (see Table 4) and end at Follow-up Visit 3; the collection of vital signs will begin after informed consent is obtained and end at Follow-up Visit 1 (see Table 6).
- e A second set of vital signs will be recorded following recovery from LP.
- f Complete neurological examination every 12 months after first dose (starting at Week 52 in this table) and abbreviated neurological examination every 6 months in between. A complete neurological examination will be conducted at End of Study/Early Termination.
- g Audiologic evaluations will also be performed prior to each dose escalation (within 72 hours prior with results available at the study visit), within 72 hours prior to the subsequent visit following a dose escalation (with results available at the study visit) per Section 7.2, at 1-month intervals following a change in hearing until stable hearing is confirmed; and when indicated by a subjective hearing impairment AE of CTCAE grade 3 or higher, or at the discretion of the investigator for subjective hearing impairment AE of CTCAE grade < 3 (Section 14.1.8). Hearing impairment AE evaluation will be performed as described in Section 12.2.6.1.
- h Do not perform starting 20 January 2021 (implemented in advance of amendment 2 as there is a direct impact to subject safety).
- i Clinical laboratory blood tests include chemistry, hematology, and coagulation.
- j Only for subjects who provide separate consent for this assessment.

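### Section 18 plans no count of subjects who ever met the protocol's own hearing-change criteria, and no rule for assigning repeat or AE-triggered audiograms to a visit

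*Combined protocol and SAP*

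**What the plan says.** **Analysis.** The only audiology sentence in Section 18 (Summary of Safety Endpoints) is "Changes in audiologic testing will be summarized by visit based on accumulated data at the time of analysis". The general rule is "All analyses will be based on available data. Missing data will not be imputed", so the denominator at each visit is whoever was tested then. Section 18 also says "counts and proportions (N, %) will be provided for categorical variables", but names no categorical hearing variable. It mentions a separate analysis plan only for pooled analyses.

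**Definition.** Section 12.2.6.1 gives three criteria for a clinically significant change from baseline: a rise of at least 20 dB at one frequency, a rise of at least 10 dB at two adjacent frequencies, or lost response at three consecutive frequencies. Section 18 uses none of them.

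**Timing.** Tables 4 to 6 place audiograms at Screening, Week 26, every 6 months, End of Study/Early Termination (EOS/ET) and follow-up. The footnotes add tests around dose escalation, tests prompted by a hearing AE, and repeats "at 1-month intervals following a change in hearing until stable hearing is confirmed". On leavers, Table 5 says "All subjects who discontinue protocol treatment will be requested to return to the clinic to complete an Early Termination Visit".

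**AE route.** Section 18 also plans "The number (n) and percentage (%) of subjects with at least 1 TEAE by system organ class and preferred term", with further tables by severity and by relationship.

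**Nature of the harm.** Section 7.3 states that "it is expected that subjects may experience some degree of nonreversible hearing loss".

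**The concern.** If a loss may be permanent, the safety question is how many treated subjects were ever affected, and by when. A row of subjects tested at one visit answers a different question: what share of those still attending has a change now. The two can differ when leaving is related to hearing, and the text makes that plausible. Section 7.2 discontinues subjects who cannot tolerate the lowest dose. Section 15.1 makes continuation after 21 June 2021 depend on judged benefit and on understanding the risks, with hearing loss named.

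The monthly repeats and AE-prompted tests are obtained because a change has been seen or suspected, so they are among the most informative audiograms. Up to five monthly repeats fit between two 6-monthly tests (26 ÷ (52/12) − 1 = 5). Without an assignment rule, it is left to the time of analysis whether they count, and which one represents a visit.

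**Working it through.** The plan gives no hearing-loss rate, dropout rate or precision target for this study, and the figure of about 60 subjects has no calculation behind it. There is no planned figure to reproduce.

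**Step 1. Does an audiogram that meets the criteria reach a cumulative table?**
- Section 12.2.4 sends new abnormal physical findings to the AE record, and Section 12.2.5 does so for clinically significant neurological changes (with exceptions).
- Section 12.2.6.1 has no such sentence. Sections 12.2.2 and 14.1.8 run the other way: a hearing AE of grade 3 or higher requires an audiogram.
- A change found by audiogram and not reported as an AE therefore appears only in the by-visit summary.
- Reported hearing AEs are counted per subject, but may be split over preferred terms. No combined summary of this AE of special interest is planned.

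**Step 2. How far can a by-visit row lie from the share ever affected?** All rates here are assumptions. Per 6 months, a fraction h of unaffected subjects meets the criteria, d0 of unaffected and d1 of affected subjects leave, and loss is permanent. Start with U = 1 and A = 0 and take four steps to Week 104:
- new = h·U; then U ← U − new and A ← A + new
- row = A/(A + U)
- leaving: U ← U(1 − d0), A ← A(1 − d1)
- ever affected = sum of new ÷ starting cohort

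With h = 0.12 and d0 = 0.05:
- New cases per step: 0.1200, 0.1003, 0.0839, 0.0701. The sum is 0.374 (37%), or 22.5 of 60.
- Unaffected at the Week 104 test: 0.88⁴ × 0.95³ = 0.5142.
- d1 = 0.20: A runs 0.1200, 0.1963, 0.2409, 0.2629. Row = 0.2629/(0.2629 + 0.5142) = 34%.
- d1 = 0.40: A runs 0.1200, 0.1723, 0.1873, 0.1825. Row = 0.1825/(0.1825 + 0.5142) = 26%.
- If leaving comes before the test in each interval: (0.2629 × 0.8)/(0.2629 × 0.8 + 0.5142 × 0.95) = 30%, and (0.1825 × 0.6)/(0.1825 × 0.6 + 0.5142 × 0.95) = 18%.
- Equal leaving, d1 = 0.05: row = 1 − 0.88⁴ = 40%.

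The same steps for other incidences, with d0 = 0.05 throughout:

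| h | Ever affected | Row, d1 = 0.05 | Row, d1 = 0.20: leave after / before test | Row, d1 = 0.40: leave after / before test |
|---|---|---|---|---|
| 8% | 26% | 28% | 23% / 20% | 18% / 12% |
| 12% | 37% | 40% | 34% / 30% | 26% / 18% |
| 20% | 56% | 59% | 52% / 48% | 42% / 31% |

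Under equal leaving the row exceeds the crude ever-proportion, because unaffected leavers stay in the latter's denominator with short follow-up. This is why the crude proportion needs cumulative incidence beside it.

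**Step 3. Precision of the missing count.** Exact (Clopper-Pearson) 95% intervals with 60 subjects, at assumed counts: 6/60 = 10% (3.8 to 20.5); 15/60 = 25% (14.7 to 37.9); 30/60 = 50% (36.8 to 63.2). These are wide, but informative for a descriptive study.

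**The case against.** Four stronger readings are tempting, and the documents do not support them.

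- **A reader might infer that no figure shows how many subjects ever lost hearing.** The TEAE table does count subjects with a reported hearing AE, and someone whose hearing AE led to stopping stays counted. The AE definition in Section 14.1.1 is also broad enough for an investigator to record an audiometric change. What remains is that recording is not required, so the count depends on reporting practice.
- **A reader might infer that triggered audiograms have no place in the by-visit table.** The laboratory sentence is limited to scheduled times ("Laboratory test results will be summarized by baseline and change from baseline to each scheduled assessment time with descriptive statistics"); the audiology sentence carries no such limit. Dosing visits occur every 2 weeks with a window of ±1 week, so an on-treatment audiogram can be matched to some visit, and escalation tests are already tied to dosing visits. What is missing is the rule.
- **A reader might infer that leavers with loss disappear.** Audiograms are scheduled at EOS/ET and at follow-up 2 weeks later, and these capture some of them. The EOS/ET row, however, pools very different exposure times and is not a cumulative count.
- **A reader might infer that the by-visit figure is biased low.** No document gives a dropout rate or shows that leaving depends on hearing. With equal leaving the row is slightly higher than the share ever affected.

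It is also fair to say that Section 7.3 presents nonreversible loss as something subjects may experience, and says the drug's share cannot be separated from disease progression. Audiology is a secondary, descriptive endpoint.

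**Conclusion.** The point holds as an omission. Section 18 applies none of the Section 12.2.6.1 criteria, plans no subject-level cumulative count from the audiograms, and gives no rule for placing monthly-repeat or AE-prompted tests. The TEAE table covers part of the gap, namely loss that was reported as an AE. This conclusion rests on the text alone and needs no assumed rate.

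The size of any understatement is conditional. With 12% incidence and 5% leaving among the unaffected per 6 months, the Week 104 row falls 4 to 19 percentage points below the 37% ever affected if affected subjects leave at 20% to 40%. It lies about 3 points above if they leave at the same 5%. The illustration also sets aside what the EOS/ET and follow-up audiograms would recover. It shows that the by-visit table cannot be relied on for this question, not that it will be wrong in a known direction. The change should be made before the analysis, but nothing here invalidates the study.

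**What to change.** In Section 18, keep the by-visit table as supportive and add a main hearing summary that uses every scheduled, triggered, repeat, EOS/ET and follow-up audiogram:
- n (%) of treated subjects with a post-baseline audiogram who ever met each Section 12.2.6.1 criterion, with exact 95% intervals, and the number of treated subjects without such an audiogram;
- each subject's worst change from baseline;
- cumulative incidence of first meeting the criteria at Weeks 26, 52 and 104;
- a visit-window rule that says which audiogram represents a visit when several fall in one window;
- a cross-tabulation of meeting the criteria against having a hearing TEAE, with the hearing preferred terms combined.

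The cost is a paragraph and a small set of tables from data the protocol already collects. The hearing figure may be less favourable. Two limits should be stated beside it: the count still mixes drug and disease loss, and it excludes loss before this study's baseline, which matters for subjects who entered already on adrabetadex.
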